**PROSPECT: PROSPECTIVE STUDY FOR SYMPTOMATIC RELIEF OF
ESSENTIAL TREMOR WITH CALA THERAPY**

**PROTOCOL ET-14
REV A; 22 JUNE 2018**

Cala Health, Inc.
[name]
[name]

CLINICAL STUDY SYNOPSIS

| Study Objective | |
|------------------------|--|
| Title | PROSPECT: PROspective study for SymPtomatic relief of Essential tremor with Cala Therapy |
| Study Device | Cala TWO Device |
| Objective | The study objective is to evaluate symptomatic hand tremor relief in the treated hand following stimulation with the Cala TWO device in adults with essential tremor over a 3-month duration |

| Study Design Elements | |
|------------------------------|--|
| Study Design | Prospective, multi-center, single-arm, non-significant risk study designed to evaluate the Cala TWO device. Subjects will be screened for eligibility and fitted with a Cala TWO device. Subjects will wear the device at home for a period of 3 months, during which they will be asked to stimulate their dominant hand twice a day. The stimulation amplitude will be based on each subject's stimulation threshold. Subjects will have in clinic assessments at enrollment, month 1 and 3. |
| Effectiveness Endpoints | 
The effectiveness of the Cala TWO device in reducing essential tremor symptoms will be evaluated by the following:
 
Co-Primary Effectiveness Endpoints
 
 • TRG Essential Tremor Rating Assessment Scale (TETRAS) subset score, relevant to the stimulated upper limb, change from pre-stimulation at baseline to post-stimulation at 3 months. • Bain & Findley Activities of Daily Living (ADL) scale subset score, relevant to the stimulated upper limb, change from pre-stimulation at baseline to post-stimulation at 3 months. 
Secondary Effectiveness Endpoint
 
 • Tremor power, as collected with the device during postural holds, change from pre-stimulation to post-stimulation across sessions. 
Additional Exploratory Analyses
 
 • Quality of Life in Essential Tremor Questionnaire (QUEST) • Clinician/Patient Global Impression of Severity (C/PGI-S) • Clinician/Patient Global Impression of Improvement (C/PGI-I) • Patient Session Impression of Improvement (PSI-I) • TETRAS – subset relevant to non-stimulated upper limb • TETRAS and ADL pre- versus post-stimulation within each visit • Product Survey • Device usage metrics |
| Safety Endpoint | The safety of the Cala TWO device will be evaluated by the incidence of device and therapy-related adverse events. Additionally, all adverse events documented during study conduct will be tabulated and reported. |

| | |
|---------------------|--|
| Number of Subjects | Up to 500 subjects |
| Number of Sites | Up to 40 US sites |
| Study Participation | The length of study participation is 3 months +/- 2 weeks |
| Follow-up Schedule | Enrolled subjects will return to the site at 1 month +/- 1 week and 3 months +/- 2 weeks from enrollment |

| Subject Population | |
|--------------------|--|
| Inclusion Criteria | 
Prospective subjects must meet all of the following criteria to be eligible for study participation:
 
 • Must be ≥ 22 years of age • Competent and willing to provide written, informed consent to participate in the study • A diagnosis of essential tremor as confirmed from clinical history and examination by a movement disorder neurologist • A tremor severity score of 2 or above in the dominant hand/arm as measured by any one of the TETRAS upper limb items and a minimum subset score of 6 across all upper limb items • Significant disability due to essential tremor (Bain & Findley score of 3 or above in any one of the upper limb items and a minimum subset score of 8 across all upper limb items) • Stable dose of tremor medications, if applicable, for 30 days prior to study entry • Stable dose of antidepressant medications, if applicable, for 90 days prior to study entry • Willing to comply with study protocol requirements including: 
 ○ remaining on a stable dosage of tremor and antidepressant medications, if applicable, during the duration of the study ○ no significant alcohol or caffeine consumption within 8 hours prior to study visits ○ no usage of the Cala TWO device within 8 hours prior to study visits |
| Exclusion Criteria | 
Prospective subjects who meet any of the following criteria are not eligible for enrollment in this study:
 
 • Moderate to severe ethanol dependence as defined by the criteria outlined in the DSM-5 (score of 4 or higher) |

- Implanted electrical medical device, such as a pacemaker, defibrillator, or deep brain stimulator, or implanted metal in the wrist to be stimulated
- Previous thalamotomy procedure, including stereotactic thalamotomy, gamma knife radiosurgical thalamotomy, and focused ultrasound for the treatment of tremor
- Suspected or diagnosed epilepsy or other seizure disorder
- Swollen, infected, inflamed areas, or skin eruptions, open wounds, or cancerous lesions of skin at stimulation site
- Peripheral neuropathy affecting the tested upper extremity
- Presence of any other neurodegenerative disease like Parkinson-plus syndromes suspected on neurological examination. These include: multisystem atrophy, progressive supranuclear palsy, dementia with Lewy bodies, and Alzheimer's disease.
- Anyone suspected to have the diagnosis of idiopathic Parkinson's disease (PD). This includes excluding anyone with the presence of parkinsonian features including bradykinesia rigidity, or postural instability. Subjects who exhibit only mild resting tremor but no other symptoms or signs of PD may be included.
- Botulinum toxin injection for hand tremor within 6 months prior to study enrollment
- Are participating or have participated in another interventional clinical trial in the last 30 days which may confound the results of this study, unless approved by the Sponsor
- Significant alcohol or caffeine consumption within 8 hours prior to study enrollment, which may confound the results of the study, where significant caffeine is considered more than 95 mg (equivalent to a cup of coffee), and significant alcohol is considered more than 14 g (equivalent to 5 oz of wine, 12 oz of beer, or 1.5 oz of distilled spirits).
- Subjects unable to communicate with the investigator and staff
- Any health condition that in the investigator's opinion should preclude participation in this study
- Pregnancy or anticipated pregnancy during the course of the study

Study Contacts**Sponsor**

Cala Health, Inc.
[name]
[name]

Contact: [name], MS
Clinical Program Manager
[contact]
[contact]

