## **1 STUDY OVERVIEW**

### **1.1 Design and Objective**

This is a prospective, multi-center, single-arm, non-significant risk study designed to evaluate the Cala TWO device. Subjects will be screened for eligibility and fitted with a Cala TWO device. Subjects will wear the device at home for a period of 3 months, during which they will be asked to stimulate their dominant hand twice a day. The stimulation amplitude will be based on each subject's stimulation threshold. Subjects will have in clinic assessments at enrollment, month 1 and 3.

The study objective is to evaluate symptomatic hand tremor relief in the treated hand following stimulation with the Cala TWO device in adults with essential tremor (ET) over a 3-month duration.

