## 2 STATISTICAL METHODS

### 2.1 General Principles

- All hypothesis testing will be performed using a two-sided test at a 0.05 level of significance or a one-sided test at a 0.025 level of significance. P-values will be rounded to three decimal places. If a p-value is less than 0.001 it will be reported as “< 0.001.”
- Summary statistics will be reported for all analyzed variables.
  - Continuous data will be summarized using descriptive statistics: mean, standard deviation, median, and interquartile range (first and third quartiles).
  - Categorical, non-ordered variables will be summarized using frequency counts and percentages.
  - Ordinal variables, including those specific to study outcomes – e.g., the TRG Essential Tremor Rating Assessment Scale (TETRAS) and the Bain & Findley Activities of Daily Living (ADL) scale -- will be summarized using measures of central tendency and variance as opposed to frequency counts and percentages; that is, these variables will be reported using the same metrics as defined above for continuous variables.
- For events which can occur more than once in a single subject (e.g., adverse events), the percentage will be based on subjects experiencing the event, and both subject and event counts will be reported.
- Baseline is defined as the last measurement for the outcome of interest obtained before the exposure to study treatment.
- For time-to-event analyses, complete dates for events of interest (e.g., index treatment, outcome events, censoring), will always be used. Incomplete dates will be incorporated by defining the event as occurring on the earliest date possible given the incomplete information. E.g., a date of UNK-FEB-2018 will be incorporated into the analysis as 01-FEB-2018.
- Statistical analyses will be performed in SAS (SAS Institute, Cary, N.C.) version 9.3 or later, R (R Foundation for Statistical Computing, Vienna, Austria) version 3.2 or later, Matlab (The MathWorks, Inc., Natick, MA) version R2016B or later, Python (Anaconda, Inc., Austin, TX) version 3.6.6 or later, or in another validated statistical software package.

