### **2.3 Co-Primary Endpoints**

Two co-primary endpoints are defined: dominant hand (DH) upper-limb performance on the TRG Essential Tremor Rating Assessment Scale (TETRAS), and the Bain & Findley Activities of Daily Living (ADL) scale. Statistical testing of each primary endpoint will be based on the cohort of all enrolled and treated subjects for whom outcome data are available.

The statistical objective related to each primary endpoint is to demonstrate that essential tremor is reduced from baseline under treatment with the Cala TWO device. Formally, the null and alternative hypotheses to be tested for each primary endpoint are as follows:

$$\begin{aligned} H_0: \mu_T &\geq 0 \\ H_A: \mu_T &< 0 \end{aligned}$$

where  $\mu_T$  is the raw change in the rating score from pre-stimulation at baseline to post-stimulation at three months in the endpoint in question.

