### **2.7 Effectiveness Outcomes**

The effectiveness of the Cala TWO device in reducing essential tremor symptoms will be evaluated by the following:

Co-Primary Effectiveness Endpoints

---

- TRG Essential Tremor Rating Assessment Scale (TETRAS) subset score, relevant to the stimulated upper limb, raw change from pre-stimulation at baseline to post-stimulation at 3 months.
- Bain & Findley Activities of Daily Living (ADL) scale subset score, relevant to the stimulated upper limb, raw change from pre-stimulation at baseline to post-stimulation at 3 months.

These endpoints will be tested statistically using hypotheses as defined above and converted to percent tremor reduction as previously reported by Elble et. al. 2016.

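### Entry floors sit on both co-primary scales; unless baseline is a separate rating, selection alone makes the expected change negative and lifts each endpoint's error rate above 2.5%

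*Protocol*

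**What the plan says.** The Inclusion Criteria in the protocol synopsis set two floors. Tremor in the dominant limb must score at least 2, "as measured by any one of the TETRAS upper limb items and a minimum subset score of 6 across all upper limb items". Disability must reach a "Bain & Findley score of 3 or above in any one of the upper limb items and a minimum subset score of 8" over the upper-limb items.

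The co-primary endpoints use the upper-limb subsets of the same two scales. In SAP 2.3 the tested quantity "is the raw change in the rating score from pre-stimulation at baseline to post-stimulation at three months in the endpoint in question". The hypotheses are H0: mu_T >= 0 against HA: mu_T < 0, and the stated aim is "to demonstrate that essential tremor is reduced from baseline under treatment with the Cala TWO device". SAP 2.7 also converts the changes to percent tremor reduction. The study has one arm and no randomization (SAP 1.1, 1.3).

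On the baseline value, SAP 2.1 says: "Baseline is defined as the last measurement for the outcome of interest obtained before the exposure to study treatment". On visits, SAP 1.1 says: "Subjects will have in clinic assessments at enrollment, month 1 and 3". Neither document says that the baseline rating is separate from the eligibility rating, or that it is the same one. The SAP also does not say whether one or both co-primary endpoints must be met.

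**The concern.** A floor on a score measured with error selects partly on the error. A candidate whose usual score is just below the floor gets in on a bad day or after a generous rating. One whose usual score is just above it is turned away on a good day. Among those enrolled, the error in the qualifying rating is therefore positive on average. The month-3 rating was not used for selection and has no such error. If the qualifying rating is also the baseline, the mean change is below zero even when tremor is stable and the device does nothing.

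No control arm is there to absorb that fall, and the benchmark is exactly zero. H0 then does not stand for no reduction in tremor, even on the SAP's own limited aim of reduction from baseline. This is distinct from the general lack of a control: it comes from one selection rule and can be reduced without adding an arm.

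**Working it through.** The plan gives no power, SD or reliability figure, so there is nothing of its own to reproduce.

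**From the documents.** Floors on both scales; test against zero at one-sided 0.025 or two-sided 0.05 (critical value 1.960 either way); up to 500 subjects.

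**Assumed.** Normal scores with pre-selection SD 1; stable tremor; inert device; the qualifying rating is the baseline; reliability r of 0.95, 0.90 or 0.80; share of candidates passing of 75% or 90%. The any-one-item rules are ignored.

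**Step 1: one scale with its own floor.** Let p be the share passing, z the cutoff and L = phi(z)/p.
- Expected fall = (1 - r) x L
- SD of change = sqrt[(1 - r)^2 x V + 1 - r^2], with V = 1 + zL - L^2
- P(reject) = Phi(d x sqrt(n) - 1.96), with d = fall / SD of change

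For p = 0.75: z = -0.674, phi(z) = 0.318, L = 0.424, V = 0.535. At r = 0.90 the fall is 0.10 x 0.424 = 0.042 and the SD of change is sqrt(0.01 x 0.535 + 0.19) = 0.442, so d = 0.096. At n = 500, Phi(0.096 x 22.36 - 1.96) = Phi(0.18) = 57%. At r = 0.95 and 0.80 the results are 32% and 87%.

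**Step 2: both floors, as the protocol has them.** Step 1 is too severe for this trial if the 75% refers to candidates who pass both floors, because each floor alone then excludes fewer. I took true scores correlated 0.5 between scales, independent rating errors and a common cutoff set so that the stated share passes both. With 75% passing both, about 85% pass each. The mean and SD of change were simulated from 4,000,000 candidates per case and put into the same P(reject) formula. With independent errors the two changes are almost uncorrelated, so the joint probability is close to the square of the single one (for example 0.39^2 = 0.15). At n = 500:

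| Pass both | r | Fall (SD) | d | Per endpoint | Both endpoints |
|---|---|---|---|---|---|
| 75% | 0.95 | 0.012 | 0.037 | 13% | 2% |
| 75% | 0.90 | 0.023 | 0.052 | 21% | 5% |
| 75% | 0.80 | 0.047 | 0.075 | 39% | 15% |
| 90% | 0.95 | 0.005 | 0.017 | 6% | 0.3% |
| 90% | 0.90 | 0.011 | 0.024 | 8% | 0.6% |
| 90% | 0.80 | 0.021 | 0.034 | 11% | 1.3% |

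With 250 subjects and 75% passing both, the rates are about 8%/13%/22% per endpoint and 0.7%/1.7%/4.8% for both.

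**Step 3: the extremes.** If 20% of candidates fail each floor taken alone and r = 0.80, simulation at n = 500 gives 58% and 57% per endpoint and 33% for both; at n = 200, about 28% and 27%, and 8%. If only 2% fail a single floor, the step 1 formula gives 3.7% to 6.3% at n = 500 for r from 0.95 down to 0.70.

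**Step 4: size in points.** If the SD were 3 points (an assumption), the 75% rows give 3 x 0.012 to 3 x 0.047, or about 0.04 to 0.14 points.

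**Step 5: effect of a separate baseline.** With baseline error independent of the qualifying rating, the expected fall is zero and simulated rejection per endpoint was 1.4% to 4.3%, centred near 2.5% (1,000 runs per setting). If half the error variance is shared within a day, a same-day re-rating leaves half the fall. In the step 1 case with r = 0.80, the fall drops from 0.085 to 0.042 and rejection from 87% to about one third.

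**The case against.** The strongest objection is that the key premise is inferred. Only a protocol synopsis is available, without a schedule of assessments. It says that subjects are screened and fitted but not when. The SAP 2.1 rule allows for several pre-exposure ratings, and if an eligibility rating precedes a separate enrollment rating, that rule already picks the later one. This stands, so the point has to be conditional. A reader might infer that the documents make the qualifying rating the baseline; they only fail to rule it out.

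Two other strong readings also go too far. A reader might take the entry scores to be high, but they are floors, and the documents give no scale maximum, mean or screen-failure share. A reader might also conclude that the error rate is well above 2.5%, or that the trial will succeed on selection alone. The 32%/57%/87% of step 1 treat one scale gated alone at 75%. With both floors the figures are much lower, 500 is a ceiling, and a both-must-succeed rule brings the joint rate below 2.5% in several cases. Against that, the SAP tests each endpoint without stating such a rule, and errors shared between scales on a bad day would raise the joint rate.

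The protocol also lists within-visit pre- versus post-stimulation TETRAS and ADL, and tremor power is the secondary endpoint. Neither depends on the gated baseline in this way. They are useful support but do not repair the co-primary test.

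Finally, a mandatory model-based corrected test would be fragile. Month-1 to month-3 variation includes real change and differing response to treatment, and a truncated distribution is hard to fit to four simultaneous item and subset rules on ordinal scales. That objection is accepted.

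**Conclusion.** The concern holds conditionally. If the qualifying rating is the baseline, the expected change under an inert device is below zero, and each endpoint's one-sided error exceeds 2.5% whenever the floors exclude anyone and reliability is below 1. The direction is certain. The size is not, because it rests on the assumed screen-failure share, reliability, between-scale correlation and evaluable number. Over the both-floors cases tabulated at 500 subjects it runs from about 6% to 39% per endpoint, and from under 1% to 15% if both must succeed. The distortion of the reported reduction in points is likely small, so the point bears mainly on the test against zero. It is worth correcting because the correction is cheap, but the documents do not show that selection would account for a positive result.

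**What to change.** 1. In SAP 2.1, define the co-primary baseline as a pre-stimulation TETRAS and ADL rating taken after eligibility is confirmed and not used to establish it. Where a screening contact already exists, use a different day, since a same-day re-rating removes only part of the bias. If a separate rating is already taken, one sentence saying so settles this item.
2. In SAP 2.3, add a sensitivity analysis, not a mandatory test. Report the raw change and percent reduction with and without a regression-to-the-mean correction over a stated range of reliability. Half the variance of the difference between month-1 and month-3 pre-stimulation scores can serve as an upper bound on rating-error variance; those visits also follow at least 8 hours off the device. If the result does not survive the correction, limit the claim accordingly.
3. Record how many candidates the floors exclude. The correction needs that share, and SAP 2.4 accounts only for enrolled subjects.
4. State in SAP 2.3 whether both co-primary endpoints must succeed.

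The cost is a few minutes of repeat rating per subject, which changes the visit procedures as well as the SAP wording, and a short extra analysis. The reported reduction becomes slightly smaller and its interval slightly wider. Placebo response and rater expectation remain unaddressed in a single-arm design.

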## **1 STUDY OVERVIEW**

### **1.1 Design and Objective**

This is a prospective, multi-center, single-arm, non-significant risk study designed to evaluate the Cala TWO device. Subjects will be screened for eligibility and fitted with a Cala TWO device. Subjects will wear the device at home for a period of 3 months, during which they will be asked to stimulate their dominant hand twice a day. The stimulation amplitude will be based on each subject's stimulation threshold. Subjects will have in clinic assessments at enrollment, month 1 and 3.

The study objective is to evaluate symptomatic hand tremor relief in the treated hand following stimulation with the Cala TWO device in adults with essential tremor (ET) over a 3-month duration.

### **1.2 Analysis Set**

Available data on all enrolled subjects will be summarized and reported, referred to in ICH E9 (“Statistical Principles for Clinical Trials”) as the *full analysis set*.

### **1.3 Randomization**

The study is non-randomized.

## 2 STATISTICAL METHODS

### 2.1 General Principles

- All hypothesis testing will be performed using a two-sided test at a 0.05 level of significance or a one-sided test at a 0.025 level of significance. P-values will be rounded to three decimal places. If a p-value is less than 0.001 it will be reported as “< 0.001.”
- Summary statistics will be reported for all analyzed variables.
  - Continuous data will be summarized using descriptive statistics: mean, standard deviation, median, and interquartile range (first and third quartiles).
  - Categorical, non-ordered variables will be summarized using frequency counts and percentages.
  - Ordinal variables, including those specific to study outcomes – e.g., the TRG Essential Tremor Rating Assessment Scale (TETRAS) and the Bain & Findley Activities of Daily Living (ADL) scale -- will be summarized using measures of central tendency and variance as opposed to frequency counts and percentages; that is, these variables will be reported using the same metrics as defined above for continuous variables.
- For events which can occur more than once in a single subject (e.g., adverse events), the percentage will be based on subjects experiencing the event, and both subject and event counts will be reported.
- Baseline is defined as the last measurement for the outcome of interest obtained before the exposure to study treatment.
- For time-to-event analyses, complete dates for events of interest (e.g., index treatment, outcome events, censoring), will always be used. Incomplete dates will be incorporated by defining the event as occurring on the earliest date possible given the incomplete information. E.g., a date of UNK-FEB-2018 will be incorporated into the analysis as 01-FEB-2018.
- Statistical analyses will be performed in SAS (SAS Institute, Cary, N.C.) version 9.3 or later, R (R Foundation for Statistical Computing, Vienna, Austria) version 3.2 or later, Matlab (The MathWorks, Inc., Natick, MA) version R2016B or later, Python (Anaconda, Inc., Austin, TX) version 3.6.6 or later, or in another validated statistical software package.

### 2.2 Analysis Populations

As stated in section 1.2, available data on all enrolled subjects will be summarized and reported, referred to in ICH E9 (“Statistical Principles for Clinical Trials”) as the *full analysis set*.

---

Two analysis populations will be defined, one consisting of all available data evaluated under ITT principles. For this purpose, “available data” means that missing data will not be replaced or imputed, and that endpoints defined as change scores (e.g., the co-primary endpoints) require both baseline and follow-up data to be present to be included in analyses.

For the ITT population, consented subjects who withdraw consent prior to device assignment, or who are found not to meet the inclusion/exclusion criteria prior to device assignment (e.g. not enrolled) will not be included in the intent-to-treat (ITT) population.

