### **2.4 Subject Disposition and Accountability**

Subject disposition will be presented in a table and flow diagram depicting the disposition of all enrolled subjects, including the number enrolled, the number who completed the study and the number and reasons of those who discontinued.

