### **2.9 Missing Data**

The primary analysis cohort will be the full analysis set as defined above. Missing data will not routinely be replaced or otherwise imputed.

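### Both co-primary tests drop every subject without a month-3 score, and the SAP plans no missing-data sensitivity analysis; in this single-arm trial, relief is overstated if poorer responders are likelier to be lost.

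*SAP*

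**What the plan says.** SAP 2.3 defines each co-primary endpoint (TETRAS and Bain & Findley ADL upper-limb subset scores) as the change from the baseline pre-stimulation score to the month-3 post-stimulation score. Each is tested in the "cohort of all enrolled and treated subjects for whom outcome data are available". SAP 2.2 makes the rule explicit: "endpoints defined as change scores (e.g., the co-primary endpoints) require both baseline and follow-up data to be present to be included in analyses". The same section places this under ITT principles, and SAP 2.9 adds that "The primary analysis cohort will be the full analysis set as defined above". SAP 1.2 and 2.2 describe that set as the available data on everyone enrolled.

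On imputation, 2.2 states that "missing data will not be replaced or imputed". SAP 2.9 states: "Missing data will not routinely be replaced or otherwise imputed". It gives no rule for exceptions. Those two sentences of 2.9 are the whole section.

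Three other places bear on the point:

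- SAP 2.4 will report "the number who completed the study and the number and reasons of those who discontinued".
- The protocol synopsis lists within-visit comparisons of TETRAS and ADL before and after stimulation, but only as exploratory analyses.
- SAP 2.2 announces two analysis populations and describes one. Nothing says that the other concerns missing data.

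**The concern.** The hypothesis in SAP 2.3 is that mean change is zero or worse, and there is no comparator. In a randomised trial, similar selective loss in both arms partly cancels. Here all of it enters the tested mean. Subjects are asked to stimulate twice a day at home for three months, so it is plausible, though not established by the documents, that those who notice little benefit are likelier to miss the last visit.

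If so, the mean change is biased toward benefit. The bias passes into the figure readers will remember, because SAP 2.7 has the endpoints "converted to percent tremor reduction". Labels such as ITT and full analysis set suggest that the estimate describes everyone treated, when it describes those who returned at month 3. Nothing planned would show how much worse the missing subjects would have to be before the conclusion changed.

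**Working it through.** **Inputs from the documents.** The design is single-arm. SAP 2.1 allows "a one-sided test at a 0.025 level of significance" or a two-sided test at 0.05; the critical value is 1.960 either way. Visits are at enrollment, month 1 and month 3. Up to 500 subjects may be enrolled, which is a cap and not a derived sample size. No dropout rate, SD, effect size or power is given, so there is no figure of the plan to reproduce.

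**Assumed inputs.** Change is in SD units, negative meaning relief. *d* is the fraction without a month-3 score. *g* is how much worse the missing subjects' mean is than the observed subjects' mean.

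**1. Direction and size of bias.** The whole-cohort mean is (1 − d) × observed mean + d × missing mean, so

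observed mean − whole-cohort mean = −d × g.

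The bias is zero if g = 0, toward benefit if g > 0, and away from benefit if g < 0.

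**2. Dropout related to month-1 change.** Assume a true change of -0.50 SD, a month-1/month-3 correlation of 0.6, and log-odds of dropout rising by 0.5 or 1.0 per SD of worse month-1 change. The overstatement is the available-case mean divided by -0.50, minus 1.

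| Dropout | Available-case mean (slope 0.5 / 1.0) | Overstatement |
|---|---|---|
| 5% | -0.514 / -0.528 | 2.8% / 5.6% |
| 10% | -0.529 / -0.554 | 5.8% / 10.8% |
| 20% | -0.557 / -0.603 | 11.4% / 20.6% |
| 25% | -0.571 / -0.627 | 14.2% / 25.4% |

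Weaker selection does less. At slope 0.2 the month-3 gap is about 0.6 × 0.2 = 0.12 SD, so the overstatement is about 0.12d / 0.50 = 0.24d, or 1.2%, 2.4% and 4.8% at 5%, 10% and 20% dropout. If better responders leave, the sign reverses.

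**3. False-positive rate when the true whole-cohort change is zero.** For one endpoint,

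rate = Φ(−1.960 + g × d × √(N(1 − d))).

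| Gap g | d = 10%, N = 100 | d = 20%, N = 500 |
|---|---|---|
| 0.25 SD | Φ(−1.960 + 0.025 × √90) = 0.042 | Φ(−1.960 + 0.05 × √400) = 0.169 |
| 0.50 SD | Φ(−1.960 + 0.05 × √90) = 0.069 | Φ(−1.960 + 0.10 × √400) = 0.516 |

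The nominal rate is 0.025. For scale, step 2 at slope 0.5 implies a gap of 0.029 / 0.10 = 0.29 SD. At slope 1.0 with 20% dropout it implies 0.103 / 0.20 = 0.515 SD.

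**4. Tipping point.** Significance is lost when the missing subjects are worse than those observed by

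(−1.96/√n − m) / d, with n = N(1 − d) and m the observed mean.

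For N = 500 and d = 0.20, n = 400 and 1.96/√400 = 0.098.

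- m = -0.15: (−0.098 + 0.15) / 0.20 = 0.26 SD.
- m = -0.50: (−0.098 + 0.50) / 0.20 = 2.01 SD.

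**5. What the alternatives recover.**

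- *Dropout on month-1 change.* A repeated-measures model using month 1 and month 3 returns -0.499 to -0.501.
- *Same, but half the dropouts leave before month 1 (10–25% dropout).* With correlations of 0.6 (enrollment/month 1) and 0.5 (enrollment/month 3), 43–50% of the bias remains. With the enrollment-visit post-stimulation score added, 20–29% remains.
- *Dropout on the month-3 change itself (10–25% dropout).* Available-case means are -0.548 to -0.713 and the month-1/month-3 model gives -0.531 to -0.645. Shifting the missing subjects by 0.31–0.60 SD restores -0.50.
- *Assigning no change to the missing subjects.* In the month-3-driven case this gives -0.464 to -0.538, so it can still overstate relief (0.538 / 0.50 = 1.076, about 8%).

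**The case against.** The restriction is openly stated in 2.2 and 2.3, and 2.4 will report losses with reasons. A reader could multiply the reported mean by the fraction observed and get a rough no-change estimate. The difference on imputation is thin: the flat statement in 2.2 defines one population's available data, while 2.9 can be read as the general rule. Nothing in the documents shows that loss will be large or selective. The slopes of 0.5–1.0 leave out weak and reversed selection. The 0.516 error rate needs zero true change, 20% loss, a 0.5 SD gap and the full 500 subjects together. The model recovers only part of the bias when loss occurs early or depends on the month-3 response, so one tipping-point analysis might be enough.

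Much of this is fair. The magnitude is illustrative, weak selection gives only a few percent, and the error rates are per endpoint; if both co-primaries must succeed, which the SAP does not say, the joint rate cannot exceed either. The imputation wording needs only an edit. But disclosure and disposition counts do not measure sensitivity, and a hand-made no-change figure is neither tested nor reliably conservative. The model's limits argue for pairing it with a tipping-point analysis. They do not argue for having no sensitivity analysis.

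**Conclusion.** The concern holds, conditionally as worded. Both co-primary tests are available-case at month 3, and the supplied SAP plans nothing to test how far the result depends on the missing subjects. The undescribed second population does not fill the gap as written.

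The bias is the missing fraction times the observed-to-missing gap. It is zero if loss is unrelated to response and reversed if better responders leave. Under the assumptions in step 2, overstatement runs from about 3% (5% dropout, slope 0.5) to about 25% (25% dropout, slope 1.0). Significance at an observed -0.50 SD is robust; at -0.15 SD with 20% of 500 missing, a 0.26 SD gap removes it. This should be fixed. It does not show that the trial's conclusion would be wrong.

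**What to change.** 1. In SAP 2.2, 2.3 and 2.9, name one cohort: all device-assigned, treated subjects with a baseline score. Call the subset with month-3 scores the available-case set. State what the second population in 2.2 is.
2. Prespecify a likelihood-based repeated-measures model with categorical visit and unstructured covariance. The outcome is change from the baseline pre-stimulation score to the post-stimulation score at month 1 and month 3, adding the enrollment-visit post-stimulation score where collected. Test the month-3 mean at one-sided 0.025 and report the available-case result beside it. If the sponsor prefers available-case as primary, keep the model as a sensitivity analysis.
3. Because the model is unbiased only if data are missing at random, add a delta-adjusted tipping-point analysis over the whole cohort, including subjects with no post-stimulation score. Shift the missing month-3 changes toward less relief over a stated range, for example 0 to 1 SD of change. Since a large effect may not tip within that range (2.01 SD in step 4), either extend it to the tipping point or report that none was reached. Include no change from baseline as one point, without labelling it conservative.
4. Report percent tremor reduction from each analysis.
5. Make the imputation statements in 2.2 and 2.9 agree.

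**Cost.** SAP wording and slightly more programming, using visits already scheduled. The sponsor takes on an explicit missing-at-random assumption, a shift range to justify, and possibly a less favourable estimate. The no-change point understates relief by the dropout fraction if loss is unrelated to response, so it cannot stand alone.
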